6 EXPECTED TOXICITIES AND DOSING DELAYS/DOSE MODIFICATIONS

Dose delays and modifications will be made using the following recommendations. Toxicity assessments will be done using the CTEP Active Version (version 4.0) of the NCI Common Terminology Criteria for Adverse Events (CTCAE) which is identified and located on the CTEP website at:

http://ctep.cancer.gov/protocolDevelopment/electronic_applications/ctc.htm.

If possible, symptoms should be managed symptomatically. In the case of toxicity, appropriate medical treatment should be used.

All adverse events experienced by patients will be collected from the time of the first dose of study treatment, through the study and until the final study visit. Patients continuing to experience toxicity at the off study visit may be contacted for additional assessments until the toxicity has resolved or is deemed irreversible.

6.1 Anticipated Toxicities

A list of the adverse events and potential risks associated with the agents administered in this study appears below and will determine whether dose delays and modifications will be made or whether the event requires expedited reporting **in addition** to routine reporting.

6.1.1 Adverse Events for poly-ICLC

Poly-ICLC is an investigational agent; however there has been significant experience in previous clinical trials as discussed in 2.1.2.4. The safety profile has been acceptable.

These reactions have been generally mild to moderate and transient for most patients in previous studies.

CONFIDENTIAL

This document is confidential. Do not disclose or use except as authorized.

Localized reactions:

- Transient (<24 h) injection fluid accumulation
- Erythema
- Induration
- Pruritus
- Edema
- Localized rash

Systemic reactions:

Flu-like symptoms including malaise, fatigue, myalgia/arthralgia, headache, fever and chills.

Hepatobiliary Disorders:

- Alanine aminotransferase (ALT) increased
- Aspartate aminotransferase (AST) increased
- Lactate dehydrogenase (LDH) elevated
- Alkaline Phosphatase increased

Bone Marrow:

- Transient Leukocyte count decreased, Neutrophil count decreased, Platelet count decreased, and Anemia

6.1.2 Adverse Events for Personalized NeoAntigen Peptides

Localized reactions or systemic reactions are not expected, but may occur:

Localized reactions:

- Erythema
- Induration
- Pruritus
- Edema
- Localized rash

Systemic reactions:

Flu-like symptoms including malaise, fatigue, myalgia/arthralgia, headache, fever and chills.

Autoimmune diseases:

CONFIDENTIAL

This document is confidential. Do not disclose or use except as authorized.

This is a theoretical possibility for which patients will be monitored. In principle, the mechanisms that allow the immune system to recognize tumor antigens could also lead to breakdown of tolerance to native or self-antigens, generating an autoimmune reaction.

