11.1.3.1 Expected adverse event

For the purposes of this study, an adverse event is considered expected when it appears in the current adverse event list, the Investigator's Brochure, or is included in the informed consent document as a potential risk.

Refer to Section 6.1 for a listing of expected adverse events associated with the study agent(s).

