11.4 Reporting to the Study Sponsor

11.4.1 Serious Adverse Event Reporting

All serious adverse events that occur after the initial dose of study treatment, during treatment, or within 30 days of the last dose of treatment must be reported to the DF/HCC Overall Principal Investigator on the local institutional SAE form. This includes events meeting the criteria outlined in Section 11.1.2, as well as the following:

- Grade 2 (moderate) and Grade 3 (severe) Events – Only events that are unexpected and possibly, probably or definitely related/associated with the intervention.
- All Grade 4 (life-threatening or disabling) Events – Unless expected AND specifically listed in the protocol as not requiring reporting.
- All Grade 5 (fatal) Events – When the patient is enrolled and actively participating in the trial OR when the event occurs within 30 days of the last study intervention.

Note: If the patient is in long term follow up, report the death at the time of continuing review.

Participating investigators must report each serious adverse event to the DF/HCC Overall Principal Investigator within 24 hours of learning of the occurrence. In the event that the participating investigator does not become aware of the serious adverse event immediately (e.g., patient sought treatment elsewhere), the participating investigator is to report the event within 24 hours after learning of it and document the time of his or her first awareness of the adverse event. Report serious adverse events by telephone, email or facsimile to:

[name]

[REDACTED]
[REDACTED]
[REDACTED]

Within the following 24-48 hours, the participating investigator must provide follow-up information on the serious adverse event. Follow-up information should describe

CONFIDENTIAL

This document is confidential. Do not disclose or use except as authorized.

whether the event has resolved or continues, if and how the event was treated, and whether the patient will continue or discontinue study participation.

Oncovir, Inc. will be provided with a simultaneous copy of all adverse events filed with the FDA.

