11.6 Reporting to the Food and Drug Administration (FDA)

[name], PhD as IND sponsor, will be responsible for all communication with the FDA. She will report to the FDA any adverse event that is serious, unexpected and reasonably related (i.e., possible, probable, definite) to the study treatment.

Unexpected fatal or life-threatening experiences associated with the use of the investigational agent will be reported to FDA as soon as possible but in no event later than 7 calendar days after initial receipt of the information.

All other serious unexpected experiences associated with the use of the study treatment will be reported to FDA as soon as possible but in no event later than 15 calendar days after initial receipt of the information.

Events will be reported to the FDA by telephone ([name]) or by paper mail using Form FDA 3500A (Mandatory Reporting Form for investigational agents). If a faxed copy of Form FDA 3500A is requested by the agency, a paper copy will also be submitted as a follow-up. Forms are available at <http://www.fda.gov/medwatch/getforms.htm>.

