12.2 Safety Meetings

The DF/HCC Data and Safety Monitoring Committee (DSMC) will review and monitor toxicity and accrual data from this trial. The committee is composed of clinical specialists with experience in oncology and who have no direct relationship with the study. Information that raises any questions about patient safety will be addressed with the Principal Investigator and study team.

The DSMC will meet quarterly and/or more often if required to review toxicity and accrual data. Information to be provided to the committee may include: up-to-date patient accrual; current dose level information; DLT information; all grade 2 or higher unexpected adverse events that have been reported; summary of all deaths occurring within 30 days for Phase I or II protocols; for gene transfer protocols, summary of all deaths while being treated and during active follow-up; any response information; audit results, and a summary provided by the study team. Other information (e.g. scans, laboratory values) will be provided upon request.

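### Autoimmune disease, named only as a theoretical risk, sits on the list of expected events, which can cost a serious case its FDA report and a non-serious grade 2–3 case its 24-hour report

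*Combined protocol and SAP*

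**What the plan says.** Section 6.1 covers both adverse events and potential risks of the study agents. It says that its list "will determine whether dose delays and modifications will be made or whether the event requires expedited reporting". Within it, Section 6.1.2 covers the personalized peptides. That section opens with "Localized reactions or systemic reactions are not expected, but may occur", lists local and flu-like reactions, and then adds autoimmune disease under its own label: "This is a theoretical possibility for which patients will be monitored". It names no disease, grade or frequency.

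Under 11.1.3.1, "an adverse event is considered expected when it appears in the current adverse event list". The Investigator's Brochure and the consent document are alternative sources, and the reader is sent to Section 6.1 for the listing. Section 11.1.3.2 calls an event unexpected if it differs in kind, severity or rate from what those sources give.

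Three later rules use this classification:

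- Section 11.4.1 adds grade 2 and 3 events to the 24-hour report to the overall principal investigator, but "Only events that are unexpected and possibly, probably or definitely related/associated with the intervention".
- Section 11.6 has the IND sponsor report to the FDA "any adverse event that is serious, unexpected and reasonably related" to study treatment, within 7 or 15 calendar days.
- Section 12.2 names, among the material that may go to the Data and Safety Monitoring Committee (DSMC), "all grade 2 or higher unexpected adverse events that have been reported".

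**The concern.** A harm that the protocol describes as theoretical would, by a literal chain of cross-references, count as expected. Expedited reporting exists largely for harms of that kind. Safety is a primary objective, and the nursing education sheet states that the approach is new in humans.

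If the literal reading is followed, the first case of vaccine-related autoimmune disease could be filed as expected, and an expedited report that would otherwise be due would not be made under the protocol's own rule. Section 1.1 adds to the stake: a parallel glioblastoma trial runs under the same IND with the same schedule, and the two trials pool their initial patients for the safety evaluation.

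The other reactions in 6.1.2 are not affected in the same way. Local and flu-like reactions also appear in 6.1.1 for poly-ICLC, so they are expected on that ground anyway.

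**Working it through.** No arithmetic applies to the classification, so the check sets the rules side by side and runs an event through them.

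**Step 1: classification.** Autoimmune disease is in 6.1.2, 6.1.2 is part of 6.1, and 11.1.3.1 names 6.1 as the listing of expected events. By presence on the list the event is expected. Against that, 11.1.3.2 would make it unexpected if it differs from the listed information. Section 6.1.2 states no disease, grade or frequency to compare with, so that test gives no definite answer. Section 6.1.2 also calls local and systemic peptide reactions not expected, although they stand on the same list. An investigator could defend either class.

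**Step 2: consequences.** Take an autoimmune event that is at least possibly related to vaccine and occurs between the first dose and 30 days after the last. Each cell gives the outcome if the event is classed as expected, then if it is classed as unexpected.

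| Event | 24-hour report (11.4.1) | IRB office (11.5) | FDA 7/15-day (11.6) | DSMC item on unexpected events (12.2) |
|---|---|---|---|---|
| Serious, grade 2 or higher | yes / yes | yes / yes | **no / yes** | **no / yes** |
| Grade 4, not serious | yes / yes | not required | no / no | **no / yes** |
| Grade 2–3, not serious | **no / yes** | not required | no / no | **no / yes** |

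Reasons for the cells:

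- Section 11.4.1 takes in every event that meets the serious criteria of 11.1.2, and neither section sets an expectedness condition.
- Grade 4 is exempt only if it is both expected and specifically listed as exempt. The supplied text contains no such list.
- Section 11.5 sends all serious events to the IRB office.
- Section 11.6 requires seriousness, unexpectedness and relatedness together.
- A non-serious grade 2–3 event classed as expected goes only on the case report form (11.4.2), due within 10 days of the end of the cycle (12.1.2).

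No single event loses both a 24-hour report and an FDA report that it would otherwise need. Serious events lose the FDA report, and non-serious grade 2–3 events lose the 24-hour report.

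**Step 3: what remains.** Related grade 3–4 toxicity counts as a DLT whatever its expectedness, subject to the exclusions in 5.5, and DLT information may go to the DSMC. The DLT window is 49 days, unless extended for a toxicity delay. The boosts on days 78 and 134 come 78 − 49 = 29 and 134 − 49 = 85 days after it closes, and grade 2 events are never DLTs. After the window, and for grade 2 at any time, committee oversight rests on the DSMC's general toxicity review, at least quarterly, and on the External Safety Monitoring Board (ESMB), which reviews accumulated data for participant safety. Neither is limited to unexpected events.

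**The case against.** The strongest reply is that the expected reading is not forced. Section 6.1 covers potential risks as well as adverse events, so presence there need not mean expected. Section 6.1.2 itself uses the words not expected, and 6.3.3 describes grade 4 or greater vaccine toxicities as unexpected. A diagnosed disease can fairly be said to differ from a theoretical possibility under 11.1.3.2. This stands as far as it goes. It shows that the text conflicts with itself, and it does not remove the sentence in 11.1.3.1 that makes the list decisive.

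The second reply is that 11.6 does not stand alone. Section 11.3 requires compliance with FDA regulations, and 13.3 cites Title 21 Part 312. That also stands: the finding concerns what 11.6 requires as written. It does not establish that the FDA would in fact not be told.

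The third reply concerns stronger conclusions that a reader might draw:

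- A reader might infer that a serious autoimmune case could escape the 24-hour report. Section 11.4.1 rules this out.
- A reader might infer that a signal could accumulate unseen. Case report forms, DLT counting, DSMC toxicity review and ESMB review all operate without regard to expectedness. The DSMC item on unexpected events is also only one of several things that may be supplied, so no guaranteed item is lost.
- A reader might extend the point to 11.8, which asks for unanticipated events after a patient leaves the study. The documents do not define that word as meaning unexpected.

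**Conclusion.** The inconsistency is real and worth correcting. A risk described only as theoretical is placed on the list that defines expected events, other wording points the opposite way, and nothing in the protocol says which governs.

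On the literal reading there are two definite losses: the 7- or 15-day FDA report for a serious, related autoimmune case, and the 24-hour report for a related, non-serious grade 2–3 case. A third loss is conditional, since either case can drop out of an optional DSMC item. The documents do not support a claim that serious cases go unreported or that safety oversight fails.

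No numerical size can be given. The documents state no rate of autoimmune events, and an assumed rate would give the chance of an event occurring, which is not the chance of a missed report.

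The conclusion assumes that staff follow 11.1.3.1 and 11.6 as written. It also assumes that the Investigator's Brochure and consent document, which were not supplied, do not settle the classification.

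**What to change.** Make two wording changes.

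1. In 6.1.2, separate observed from theoretical risks, and label autoimmune disease as a theoretical risk that is not an expected event for reporting.
2. In 11.1.3.1, add a sentence to this effect: *An event named only as a theoretical risk (at present, autoimmune disease) is treated as unexpected for the purposes of 11.4.1, 11.6 and 12.2.*

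Check the Investigator's Brochure and consent document for consistency. Section 11.1.3.1 also makes an event expected if it appears in either, so the new sentence should apply whichever source names the risk.

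The cost is a short protocol amendment and possibly one or two more expedited reports. The fix is confined to how events are classified for reporting and proposes no change to dosing, schedule or patient management.

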6.2 Toxicity Management

- 6.2.1** Treatment with corticosteroids and antihistamines are not recommended for initial treatment, but may be instituted at the discretion of the treating physician if clinically necessary.
- 6.2.2** Local applications of cold compresses and moisturizing creams are preferable over systemic agents for the management of local reactions.
- 6.2.3** Patients who develop flu-like symptoms that are controlled with acetaminophen or non-steroidal anti-inflammatory drugs given at the discretion of the investigator may be pre-treated with acetaminophen (650 mg PO) or ibuprofen (400-600 mg PO).

6.3 Dose Modifications/Delays

- 6.3.1** If a patient develops grade 3 toxicity attributable to the vaccine, additional treatment will be withheld until the toxicity has resolved or improved to grade 1. If the toxicity constitutes a DLT as defined in 5.5, the patient will be removed from the study. If the toxicity does not fulfill the criteria of a DLT, the next vaccine administration may be delayed for a maximum duration of 14 days. If vaccine dosing has to be delayed more than 2 times because of a toxicity that is not considered a DLT, the patient will be removed from the study.
- 6.3.2** If a patient develops grade 4 toxicity attributable to the vaccine (with the exception of certain grade 4 laboratory abnormalities as defined in section 5.5), he or she will be removed from treatment.
- 6.3.3** If two or more grade 4 or greater toxicities attributable to the vaccine are observed, the trial will be suspended to investigate the causes of these (unexpected) toxicities.

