1. OBJECTIVES

1.1 Study Design

The study is an open label, phase I trial in which patients with high-risk melanoma will be immunized with up to 20 peptides that are both specific to the patient's tumor cells (i.e. – not found in their normal cells) and unique to the patient (i.e. – “personal”). These peptides are encoded by missense mutations, in-frame gene fusions and novel open reading frame mutations (collectively known as “neoantigens”) that have occurred within that patient's tumor cells and are identified through DNA and RNA sequencing. Up to 20 peptides about 20-30 amino acids in length will be prepared for each patient and will be administered together with the immune adjuvant poly-ICLC. Thus, the personalized NeoAntigen Cancer Vaccine consists of peptides + poly-ICLC and will be termed “NeoVax”.

Eligible patients will be initially entered into the trial to undergo surgery with the intent to resect all melanoma detectable clinically and on radiographic scans. Patients will be reassessed for eligibility prior to the first vaccination and will continue onto the treatment phase of the trial if secondary eligibility criteria are met.

Five patients will be entered for the initial safety evaluation (Cohort 1). If none or only 1 patient experiences a DLT on Cohort 1, an additional 10 patients will be treated at this dose to increase the likelihood of detecting serious toxicities, to complete biologic correlative endpoints and to gain preliminary experience with clinical tumor activity. If two or more patients in Cohort 1 experience dose limiting toxicity (DLT) during the first 7 weeks of treatment, then the dose of poly-ICLC will be reduced by 50% and 5 patients will be enrolled on Cohort -1. If none or only 1 patient experiences a DLT on Cohort -1, then an additional 10 patients will be enrolled as described above. If two or more patients in Cohort -1 experience a DLT, then the study will be stopped.

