In parallel and under the same IND (#15703), a second phase I trial is being conducted with NeoVax (DF/HCC # 14-362 - A Phase I Study of a Personalized NeoAntigen Cancer Vaccine with Radiotherapy Among MGMT Unmethylated, Newly Diagnosed Glioblastoma Patients). Both trials utilize early stage patients who are otherwise healthy with competent immune systems. For both trials, the NeoVax personalized peptides are being produced by the same process and released to the same specifications, identical amounts are being used and the identical amount of Hiltonol® is added. In both trials the vaccination schedule is identical and the definition of Dose Limiting Toxicities is identical. In both trials, an initial cohort of five patients is being evaluated for safety.

For the purposes of evaluation of safety in the five patient cohort for either trial, the initial patients from both trials will be combined to achieve the required 5 patient cohort. Once 5 patients from the combined trials have successfully reached the end of the DLT evaluation window (4 weeks after the last priming dose) and if fewer than two DLTs have been observed, treatment can initiate to complete the initial 5 patient cohort and for the additional 10 patients at the selected dose.

CONFIDENTIAL

This document is confidential. Do not disclose or use except as authorized.

The primary objectives of the study are to test the safety and feasibility of administering NeoVax; the secondary objectives include evaluating the immune response to the personalized neoantigens and monitoring disease recurrence.

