5.4 Dose schema and staggering of patients

5.4.1 DLT and expansion cohorts

Five patients will be entered for the initial safety evaluation (Cohort 1). If two or more patients in Cohort 1 experience dose limiting toxicity (DLT) during the first 7 weeks of treatment, then that cohort will be determined to have unacceptable toxicity; otherwise, an additional 10 patients will be treated at the initial dose to increase the likelihood of detecting serious toxicities, to complete biologic correlative endpoints, and to gain preliminary experience with clinical tumor activity. If Cohort 1 is found to have unacceptable toxicity, then 5 patients may be enrolled on cohort -1 shown below. For Cohort -1, the dose of poly-ICLC is dropped by 50% relative to Cohort 1 but the dose of peptides remains the same. If two or more patients in Cohort -1 experience a DLT, then the study will be stopped. If none or only one patient experiences a DLT on Cohort -1, then 10 additional patients will be enrolled for additional toxicity evaluation, to complete biologic correlative endpoint, and to gain preliminary experience with clinical tumor activity. If four or more patients in the expansion cohort experience dose limiting toxicity (DLT) during the first 7 weeks of treatment, then that cohort will be determined to have unacceptable toxicity and further dosing of all patients will be stopped.

Dose De-escalation Schedule 1 cycle = 22days		
	Dose Level	Dose of poly-ICLC
	- 1	0.25 mg per injection site (4 injections, total dose 1 mg Vol = 4 x 0.875 ml)
Starting Dose →	1	0.5 mg per injection site (4 injections, total dose 2 mg)

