5.5 Definition of Dose-Limiting Toxicity

Dose-limiting toxicity (DLT) is based on the CTEP Active Version (version 4.0) of the NCI Common Terminology Criteria for Adverse Events (CTCAE). DLT refers to toxicities experienced within 49 days (7 weeks) of treatment initiation (“DLT window”). If treatment has to be delayed because of a toxicity that does not fulfill the criteria of a DLT, the DLT window should be extended by that time period of delay. A DLT will be defined as follows:

1. Grade 3 or 4 toxicity that is definitely, probably, or possibly related to the administration of vaccine, excluding:
 - Transient (\leq 72 hours) flu-like syndrome;
 - Grade 3 nausea, vomiting, constipation, or diarrhea that returns to grade 2 (or lower) level within 48 hours;
 - Grade 3 rash that resolves to grade 2 or grade 1 within \leq 14 days.
2. Grade 3 or 4 abnormal laboratory value that is definitely, probably, or possibly related to the administration of vaccine if it persists for more than 7 days, requires hospitalization or medical intervention (except for Grade 3 electrolyte abnormality that lasts \leq 72 hours, is not clinically complicated, and resolves spontaneously or responds to conventional medical intervention).
3. Any grade 3 or grade 4 toxicity that is considered, in the opinion of the investigator, to be dose-limiting.
4. Any death related to study treatment.

CONFIDENTIAL

This document is confidential. Do not disclose or use except as authorized.

Management and dose modifications associated with the above adverse events are outlined in Section 6 (Expected Toxicities and Dosing Delays/Dose Modifications).

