14 STATISTICAL CONSIDERATIONS

14.1 Study Design/Endpoints

The primary goals of this Phase I trial are: a) to assess safety of the vaccine and determine the recommended dose of poly-ICLC and b) to assess the feasibility of making vaccine containing an adequate number of actionable peptides and in a timely manner.

A. To evaluate safety and tolerability of administering NeoVax in patients with high-risk melanoma.

Dose-limiting toxicity (DLT) will be defined as any of the following toxicities observed:

1. Grade-3 or -4 toxicity that is definitely, probably, or possibly related to the administration of vaccine, excluding:
 - Transient (\leq 72 hours) flu-like syndrome
 - Grade-3 injection site reaction (localized rash, erythema, edema, induration) that resolves to grade 2 (or lower) within 72 hours
 - Grade-3 nausea, vomiting, constipation, or diarrhea that returns to grade 2 (or lower) within 48 hours
 - Grade-3 rash that resolves to grade 2 or grade 1 within 14 days
2. Grade-3 or -4 abnormal laboratory value that is definitely, probably, or possibly related to the administration of vaccine if it persists for more than 7 days, requires hospitalization or medical intervention (except for Grade-3 electrolyte abnormality that lasts \leq 72 hours, is not clinically complicated, and resolves spontaneously or responds to conventional medical intervention)

CONFIDENTIAL

This document is confidential. Do not disclose or use except as authorized.

3. Any grade-3 or grade- 4 toxicity that is considered, in the opinion of the investigator, to be dose-limiting
4. Any death related to study treatment

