Five patients will be entered for the initial safety evaluation (Cohort 1). We have chosen dose escalation cohorts of 5 patients, rather than a more traditional 3+3 design, because the determination of whether to treat at a different dose in this trial is made over a longer period of time due to the staggered enrollment of patients, the time required for vaccine preparation, and the extended period for safety evaluation. These larger cohort sizes help us avoid having to pause and then restart enrollment to a dosing cohort several months later. If two or more patients in Cohort 1 experience dose limiting toxicity (DLT) during the first 7 weeks of treatment, then that cohort will be determined to have unacceptable toxicity; otherwise, an additional 10 patients will be treated at this dose level to increase the likelihood of detecting serious toxicities, to complete biologic correlative endpoints, and to gain preliminary experience with clinical tumor activity. If Cohort 1 is found to have unacceptable toxicity, then 5 patients will be enrolled on Cohort -1. If two or more patients in Cohort -1 experience a DLT, then the study will be stopped. If zero or one patient experiences a DLT in Cohort -1, then 10 additional patients will be enrolled in an expansion cohort.

The table below shows the probability of moving to the dose expansion phase (0 or 1 patients with DLT out of 5 patients) for various possible values of the true, but unknown, toxicity rate.

True rate of DLT (%)	Probability of Dose Expansion (%)
10	92
20	74
30	53
40	34
50	19
60	9

If the true probability of DLT is 10% or less, then the probability of proceeding to dose expansion is at least 92%. The probability of dose expansion is less than 50% if the true rate of dose-limiting toxicities is 32% or greater.

Minimum vaccination requirement to pass DLT observation period: A minimum of 3 vaccinations and absence of DLTs are required for a patient to complete the 7-week DLT observation period successfully.

Expansion Cohort: When the recommended dose has been determined, an expansion cohort of 10 patients will be enrolled to assess the performance of the vaccine and to gain additional information about toxicities.

CONFIDENTIAL

This document is confidential. Do not disclose or use except as authorized.

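### No stated trial-level rule responds to a single vaccine-related death, and the Cohort 1 rule as written directs expansion when the one DLT is fatal

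*Combined protocol and SAP*

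**What the plan says.** **Status of a death.** The fourth DLT criterion in sections 5.5 and 14.1 is "Any death related to study treatment". It is counted in the same way as a qualifying grade 3 event. Section 5.5 limits the count in time: "DLT refers to toxicities experienced within 49 days (7 weeks) of treatment initiation", extended only when dosing is delayed for a toxicity that is not a DLT.

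**Trial-level rules.** Each one needs more than one event before it acts:

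- Cohort 1 (1.1, 5.4.1, 14.1): two or more of five patients with a DLT is unacceptable. Otherwise, in the words of 1.1, "If none or only 1 patient experiences a DLT on Cohort 1, an additional 10 patients will be treated at this dose".
- Cohort -1 (5.4.1): "If two or more patients in Cohort -1 experience a DLT, then the study will be stopped". With zero or one, 10 more are enrolled.
- Pooled gate with the parallel glioblastoma trial (1.1): once five patients have successfully reached the end of the DLT window, "if fewer than two DLTs have been observed, treatment can initiate to complete the initial 5 patient cohort" and to treat the further 10.
- Expansion cohort (5.4.1, 14.1): four or more of 10 patients with a DLT in the first 7 weeks.
- Section 6.3.3: "If two or more grade 4 or greater toxicities attributable to the vaccine are observed, the trial will be suspended" so that the causes can be investigated. This rule has no time limit and counts toxicities, not patients.

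**Oversight.** Section 12.2 says "The DSMC will meet quarterly and/or more often if required to review toxicity and accrual data". Section 12.3 adds an external board that evaluates participant safety and reports twice a year. Sections 5.9, 11.4, 11.5 and 11.6 set duties to notify and report.

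**The concern.** Read together, these rules leave one related death without any stated consequence for the trial. In Cohort 1, and equally in Cohort -1, the text goes further than silence: with a single DLT the next step is 10 more patients at that dose, whatever the DLT was. This sits badly with 6.3.3, which describes toxicities of grade 4 or greater as unexpected and worth suspending the trial to investigate, yet asks for two of them even when the first is fatal.

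The boost doses fall on days 78 and 134 (5.3), well after day 49. A related death there enters none of the cohort rules. It counts only toward 6.3.3, where a second event is needed.

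The patients have had all detectable melanoma resected, and section 2.2 calls this population potentially curable. The nursing sheet states that the approach is new in humans. How the trial responds to a first related death should therefore be settled in writing beforehand.

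**Working it through.** **1. Reproduce the plan's own figures.** Section 14.1 takes expansion to mean zero or one DLT in five patients, so P = (1−p)^5 + 5p(1−p)^4.

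| True DLT rate | Stated | Recomputed |
|---|---|---|
| 10% | 92% | 91.9% |
| 20% | 74% | 73.7% |
| 30% | 53% | 52.8% |
| 40% | 34% | 33.7% |
| 50% | 19% | 18.8% |
| 60% | 9% | 8.7% |

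The expansion-cohort table, P(4 or more of 10), also reproduces at 5%, 10%, 20%, 30%, 36% and 40%: 0.0010, 0.0128, 0.1209, 0.3504, 0.5132 and 0.6177. The tables are right. They also confirm that one DLT of any kind passes the gate. At a 10% rate, the 92% is 0.9^5 = 59% with no DLT plus 5 × 0.1 × 0.9^4 = 33% with exactly one, and nothing separates a fatal DLT from any other.

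**2. Cohort 1, given one related death within the window.** The death is one DLT, so expansion requires no further DLT. The text allows two readings of how many other patients must be clear:

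- *Five patients in total, the death being one of them* (1.1, 5.4.1 and 14.1 as written): four others must be DLT-free, (1−p)^4.
- *Five who finish successfully* (pooled gate in 1.1 with 5.4.4, which makes absence of DLTs and at least three vaccinations conditions for finishing the period successfully): five others must be DLT-free, (1−p)^5.

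| Assumed DLT rate in the others | Four others | Five others |
|---|---|---|
| 5% | 0.95^4 = 81% | 0.95^5 = 77% |
| 10% | 0.9^4 = 66% | 0.9^5 = 59% |
| 20% | 0.8^4 = 41% | 0.8^5 = 33% |

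**3. Expansion cohort, given one related death within the window.** The four-of-10 rule is not met if at most two of the other nine have a DLT: (1−p)^9 + 9p(1−p)^8 + 36p²(1−p)^7.

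- p = 10%: 0.387 + 0.387 + 0.172 = 0.947
- p = 20%: 0.134 + 0.302 + 0.302 = 0.738

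This covers the four-of-10 rule alone. If one of those other DLTs were grade 4 or greater, 6.3.3 would suspend the trial, so the chance that neither rule acts is at most 95% and 74%.

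**4. Limits of these figures.** The rates 10% and 20% appear in both tables of 14.1, and 5% in the second. All are illustrative, and patients are taken as independent. Steps 2 and 3 start from a death that has already happened. The documents give no rate of fatal toxicity. As a pure assumption, risks q of 1%, 2% or 5% per patient would give exactly one related death among 15 patients with probability 15q(1−q)^14 = 13%, 23% or 37%.

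**The case against.** The strongest reply is that the plan does not depend on automatic rules alone. A fatal event is notified at once to the principal investigator (5.9), reported within 24 hours (11.4), sent to the IRB office (11.5) and, if unexpected, reported to FDA within 7 days (11.6). DLT information and 30-day deaths are listed among the material the DSMC may receive, and the DSMC may meet more often than quarterly (12.2). The external board, the IRB and the sponsor could also act. In practice someone would probably pause the trial. That stands as a reason to moderate the severity. It does not alter a written instruction to expand, and none of these provisions names a death as the trigger for a review or hold.

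Three stronger readings are tempting, and the documents do not support them:

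- *Late deaths are ignored.* They are outside the DLT window, but 6.3.3 has no time limit and does count them. One fatal case with a second qualifying toxicity in the same patient might even meet 6.3.3, because the unit of counting is undefined.
- *Patients could be started for a whole quarter with no one looking.* That assumes every body stays inactive and that the option of extra DSMC meetings goes unused.
- *The 81% figure is settled, or measures risk to patients.* It rests on one of two readings of the gate and is conditional on a death. The background points toward low toxicity: nothing above grade 2 in the cited long-peptide studies (2.1.1), and no grade 3 or 4 events in 11 patients given long peptides with poly-ICLC (2.1.2.4).

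It can also be said that the response to a death is a clinical and oversight decision. That is accepted, and it limits what the fix may ask for.

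**Conclusion.** The point holds in a limited form. No stated trial-level rule responds to one related death, and the Cohort 1 gate as written leads to 10 more patients at the same dose even when the single DLT is that death. Given such a death, the gate would still open with probability 81%, 66% or 41% at assumed DLT rates of 5%, 10% or 20% on the four-patient reading, and 77%, 59% or 33% on the five-patient reading. The text does not settle which reading applies. These results assume independent patients, one qualifying toxicity recorded for the fatal case, and no discretionary pause.

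No estimate, analysis or stated operating characteristic is wrong, and discretionary oversight exists. This is a recommended safety change, not an essential correction.

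**What to change.** Reconcile 1.1, 5.4.1, 5.5, 6.3.3 and 14.1 on three matters:

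- The zero-or-one-DLT gate should not direct expansion by default when the one DLT is a related death.
- A related death at any time, including the boost phase, should be tied to an unscheduled review by the existing DSMC under 12.2.
- The pooled gate in 1.1 should be squared with 5.4.4, so that it is clear whether a patient with a DLT is one of the five. Section 6.3.3 should say whether it counts events or patients.

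What hold applies, and what happens to patients already on treatment, is for the sponsor and DSMC to decide and write down. No particular rule is proposed here.

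The cost is a few sentences of protocol text and, should a related death occur, one extra meeting of a committee that already exists. The downside is possibly a short accrual pause in a rare event. The tables in 14.1 can stay, with a note that they count DLTs of every kind alike.
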